#### CL

Clearance (CL) is defined as the volume of plasma completely cleared of drug per unit time and is estimated in trials of an IV-administered drug as the dose divided by the  $AUC_{(0-\infty)}$ . It will be obtained from the **CL\_obs** parameter calculated by WinNonlin. If %AUCex is >20% or the Lambda Z Acceptance Criteria are not met, the estimated CL value will be flagged when listed in the report and will be excluded from statistical summaries of parameter estimates and downstream calculations. CL will be reported in units of L/h.

#### Vd

Volume of distribution (Vd) central is estimated in trials of an IV-administered drug of CL divided by Ke. It will be obtained from the Vz\_obs parameter calculated in WinNonlin. If %AUCex is >20% or the Lambda Z Acceptance Criteria is not met, the estimated Vd value will be flagged when listed in the report and will be excluded from statistical summaries of parameter estimates and downstream calculations. Vd will be reported in units of L/h.

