## 3.2 Study Outcome Measures

## 3.2.1 Primary

- Lung concentration o and PK parameters of total apramycin:
  - $\circ \quad ELF: C_{max}, AUC_{(0-24)}, AUC_{(0-t)}, AUC_{(0-\infty)}, C_{max}, T_{max}, t^{1/_2}$
  - o AM:  $C_{max}$ , AUC(0-24), AUC(0-t), AUC(0- $\infty$ ),  $C_{max}$ ,  $T_{max}$ ,  $t^{1/2}$
- Plasma concentration and PK parameters of total apramycin:
  - $\circ \quad AUC_{(0-\infty)}, \, AUC_{(0-t)}, \, AUC_{(0-24)}, \, C_{max}, \, T_{max}, \, t^{1\!\!/_2}, \, CL_T, \, Vd \; central,$
- Ratio of exposure parameters of Lung PK to Plasma PK:
  - $\circ$  ratio of  $C_{max}$  in ELF over  $C_{max}$  in plasma
  - $\circ$  ratio of  $C_{max}$  in AM over  $C_{max}$  in plasma
  - $\circ~$  ratio of AUC  $_{(0-24)},$  AUC  $_{(0-t)},$  and AUC  $_{(0-\infty)}$  in ELF over AUC  $_{(0-24)},$  AUC  $_{(0-t)},$  and AUC  $_{(0-\infty)}$  in plasma
  - $\circ~$  ratio of AUC  $_{(0-24)},$  AUC  $_{(0-t)},$  and AUC  $_{(0-\infty)}$  in AM over AUC  $_{(0-24)},$  AUC  $_{(0-t)},$  and AUC  $_{(0-\infty)}$  in plasma

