### **3.2.** Endpoints

#### Primary:

- Lung concentration and PK parameters of total apramycin:
  - ELF: Area under the concentration-time curve (AUC) from time of dosing to 24 h (AUC(0-24)), AUC from time of dosing to time t (AUC(0-t)), AUC extrapolated to infinity (AUC(0- $\infty$ )), maximum concentration (Cmax), time to maximum concentration (Tmax), terminal elimination half-life (t/2)
  - o AM: AUC(0-24), AUC(0-t), AUC(0- $\infty$ ), Cmax, Tmax, t1/2
- Plasma concentration and PK parameters of total apramycin:
  - $\circ$  AUC(0- $\infty$ ), AUC(0-t), AUC(0-24), Cmax, Tmax, t1/2, total clearance (CLT), volume of distribution (Vd) central
- Ratio of exposure parameters of Lung PK to Plasma PK:
  - $\circ \quad \text{ratio of } C_{max} \text{ in ELF over } C_{max} \text{ in plasma}$
  - o ratio of Cmax in AM over Cmax in plasma
  - ratio of AUC (0-24), AUC (0-t), and AUC (0-∞) in ELF over AUC (0-24), AUC (0-t), and AUC (0-∞) in plasma
  - o ratio of AUC (0-24), AUC (0-t), and AUC (0-∞) in AM over AUC (0-24), AUC (0-t), and AUC (0-∞) in plasma

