#### Ke

The terminal phase elimination rate constant (Ke) is defined as the first-order rate constant describing the rate of decrease of drug or metabolite concentration in the terminal phase (defined as the terminal region of the PK curve where drug or metabolite concentration follows first-order elimination kinetics). Ke will be computed as the slope of a terminal region consisting of  $\geq$  3 successive points in the plot of log-transformed concentration data versus time. Ke will be estimated using uniform weighting.

Timepoints used in the estimation of  $K_e$  will be initially selected using the WinNonlin automatic algorithm. Manually chosen timepoints may be used at the discretion of the PK analyst after examination of the automatically chosen points in the context of the semi-log profile to improve estimation of  $K_e$  on a case-by-case basis. The set of points chosen must satisfy the Lambda Z Acceptance Criteria described above. Otherwise, the elimination rate constant and all derived parameters (apparent terminal elimination half-life  $[t_{1/2}]$ , AUC Extrapolated to Infinity  $[AUC_{(0-\infty)}]$ , clearance [CL], and volume of distribution  $[V_d]$ ) will be treated as missing.

Drug concentration used to calculate  $K_e$  will be indicated in Listing 35. This parameter will be obtained from the Lambda\_z parameter calculated by WinNonlin. Ke will be reported in units of 1/h.

**t**½

The  $t_{1/2}$  is defined as the time required for the drug or metabolite concentration to decrease by a factor of onehalf in the terminal phase. The  $t_{1/2}$  can be estimated as  $\ln(2)/K_e$ . It will be obtained from the **HL\_Lambda\_z** parameter calculated by WinNonlin. Half-life will be reported in units of h. If the Lambda Z Acceptance Criteria is not met,  $t_{1/2}$  will be treated as missing.

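### The primary plasma endpoint called central volume of distribution is computed as the terminal-phase volume Vz, and SAP 10.2 gives it the wrong unit

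*SAP*

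**What the plan says.** **Endpoint name.** SAP 3.2 lists "volume of distribution (V d ) central" among the primary plasma parameters. The protocol does the same in its summary and in 3.2.1, where the list under "Plasma concentration and PK parameters of total apramycin" ends with Vd central.

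**Estimator.** SAP 10.2, under Vd, says that this volume "central is estimated in trials of an IV-administered drug of CL divided by" Ke, obtained from `Vz_obs` as the "parameter calculated in WinNonlin". Under Ke, the rate constant describes the "rate of decrease of drug or metabolite concentration in the terminal phase" and is taken from `Lambda_z`. Under CL, clearance is dose over AUC(0-∞).

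**Unit.** The Vd paragraph ends by stating that Vd "will be reported in units of L/h". CL is also given in L/h, and Ke "will be reported in units of 1/h".

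**Method.** Protocol 11.4.4 and SAP 10.2 plan noncompartmental analysis only.

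**Other mentions.** Protocol 11.4.4.1, both abbreviation lists, the SAP's Ke paragraph, Table 86 and Listing 38 use Vd without *central*. The two output shells head the column in L.

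**The concern.** A central volume and a terminal-phase volume are different pharmacokinetic quantities. The first relates dose to concentration before distribution into tissue. The second relates the amount in the body to plasma concentration during the terminal phase, so it includes tissue distribution. If the SAP's rule is followed exactly, the number reported against a named primary endpoint is not the quantity that the name describes. A reader could take it for a central volume and reuse it as one, for example as a starting value in a later compartmental model.

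The exposure is narrow. A report that follows Table 86 and Listing 38 would print Vd in litres, with neither *central* nor L/h. The mismatch would surface where results are set against the endpoint list or where the text of SAP 10.2 is repeated. All analyses are descriptive (Protocol 11.1, SAP 6.8). Cmax, AUC, the lung-to-plasma ratios (SAP 10.2.1) and the decision to enroll cohort T5 (Protocol 4) do not use Vd.

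**Working it through.** The plan states no figure for this parameter, so there is none to reproduce. The check is algebra on the SAP's own definitions, a unit check and an illustration of size.

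**1. What the rule computes.** With CL = Dose/AUC(0-∞) and Ke = Lambda_z,

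CL/Ke = Dose/(Lambda_z × AUC(0-∞)) = Vz.

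This holds whatever the disposition model.

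**2. When Vz equals the central volume.** Under one compartment, Lambda_z = k10 = CL/Vc, so Vz = Vc. Under two compartments, Lambda_z estimates the slower rate β, and Vz/Vc = k10/β. Because αβ = k10·k21, and α > k21 whenever k12 > 0, β is below k10 and Vz exceeds Vc.

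**3. Is a central volume estimated elsewhere?** No. There is no back-extrapolated initial concentration, no dose over C0 and no compartmental fit. Protocol 11.4.4.1 allows other PK parameters to be calculated but specifies none.

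**4. Unit.** (L/h)/(1/h) = L. The Vd paragraph's L/h conflicts with the SAP's own units for CL and Ke and with both output shells.

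**5. Size, by illustration only.** The documents give no human compartment parameters and no LLOQ. Assumed values: 70 kg subject (30 mg/kg × 70 = 2100 mg), 0.5 h infusion, CL 6 L/h, Vc 20 L, so k10 = 6/20 = 0.3 per h. Profiles are noise-free, at the protocol's post-dose plasma times (0.5 to 60 h), with linear-up log-down AUC. The terminal fit is the one with the best adjusted R², preferring more points when within 0.0001. It is accepted under the SAP rules: adjusted R² at least 0.90, span at least 3 half-lives, at least 3 points after Tmax.

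Example with k12 = 0.1 and k21 = 0.15: the rate constants sum to 0.55 and k10·k21 = 0.045. Then β = (0.55 − √(0.3025 − 0.18))/2 = (0.55 − 0.35)/2 = 0.10 per h, and k10/β = 3.00 (Vz 60 L against Vc 20 L).

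| k12, k21 (per h) | Terminal half-life (h) | Exact Vz/Vc | `Vz_obs`/Vc, LLOQ 0.01 to 0.1 µg/mL |
|---|---|---|---|
| 0 (one compartment) | 2.3 | 1.00 | 1.00 |
| 0.03, 0.6 | 2.5 | 1.09 | 1.09 |
| 0.1, 0.3 | 4.1 | 1.77 | 1.69 to 1.75 |
| 0.1, 0.15 | 6.9 | 3.00 | 2.94 |

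Every fit in the table passes, with a span of at least 4.07 half-lives and at most 1.1% of AUC extrapolated. Taking the strictly best adjusted R² moves the last row to between 2.95 and 2.96.

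If the LLOQ were 0.5 µg/mL, the last row's 3-point fit would fail (span 2.79). The SAP says "Manually chosen timepoints may be used at the discretion of the PK analyst", and the 4-, 5- and 6-point fits pass with ratios of 2.08, 1.87 and 1.75.

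The acceptance rules therefore do not detect the mismatch. They test the quality of the terminal fit and the extrapolated fraction, not which volume is being estimated.

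**The case against.** The strongest reply is that the calculation is fully specified and only a word is wrong. SAP 10.2 gives the formula, the software output and the exclusion rule, so two programmers would produce the same number. The evidence on intent also leans one way. Both abbreviation lists define Vd simply as volume of distribution, and the protocol's list also carries Vz/F. The SAP's Ke paragraph names Vd, without *central*, among the parameters derived from the terminal slope. The method is noncompartmental, the named output is `Vz_obs`, and both shells print Vd in litres. All of this stands and makes *central* most likely a stray qualifier. It does not remove the inconsistency, because the word remains in both endpoint lists and in the rule itself, and no section disowns it.

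A reader might infer that the plan promises a central volume and then omits its analysis. The documents do not support that: nothing beyond the word suggests that a compartmental or back-extrapolated estimate was intended.

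A reader might also infer that the reported value could be several-fold too large. With an assumed half-life of 16.5 h (k12 = k21 = 0.05) the best fit gives a ratio near 7, but no fit in that case meets the SAP's criteria. Vd would then be missing (Ke paragraph), or flagged and kept out of the summaries (Vd paragraph). Such a value would be reported only if the optional relaxed criteria in SAP 10.2 were invoked. Protocol 2.2 also reports no wide tissue distribution in nonclinical data. That does not establish one-compartment kinetics, but it makes large ratios less likely.

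**Conclusion.** The point holds as a minor correction. The quantity that SAP 10.2 computes is Vz, the endpoint is named as a central volume, and the two coincide only under one-compartment disposition, which neither document states or assumes. This conclusion rests on the SAP's definitions alone. The L/h unit is wrong on the same definitions.

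The size for apramycin is unknown. The range of 1.0 to about 2.9 rests on the assumed CL, Vc, rate constants and LLOQ, and shows only that a material gap can pass the acceptance rules. The consequence is confined to naming and interpreting one descriptive parameter. Its listing as a primary endpoint is the reason to correct it rather than let it pass.

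**What to change.** Issue a SAP addendum before final data lock; SAP 15 allows this and rules out amendment afterwards. It should:

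- Replace the central-volume name in SAP 3.2 and 10.2 with Vz (terminal-phase volume of distribution, CL/Lambda_z). Keep *central* only if an estimator for a central volume is actually specified.
- Change the Vd unit in SAP 10.2 from L/h to L.
- Footnote Table 86 and Listing 38 to say that Vd is Vz and not a central volume.

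In the protocol, align the summary and 3.2.1 at the next amendment, or explain the difference in the CSR. Protocol 14.2 requires approval of an amendment before use, so this wording alone does not justify one.

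The cost of the renaming route is one short addendum: wording in two SAP sections, one unit and two footnotes. It needs no new data and no new analysis. Keeping *central* would cost more, because an estimator would have to be added.

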#### 10.2.1. Ratio of Lung PK to Plasma PK

Only plasma samples collected at the same time as the BAL procedure will be used in the calculations of the Lung PK to Plasma PK ratios. The GM concentrations of apramycin in ELF, AM, and plasma from the BAL sampling timepoints will be used to estimate the population average  $C_{max}$ ,  $AUC_{(0-\infty)}$ ,  $AUC_{(0-24)}$ , and  $AUC_{(0-last)}$ .  $AUC_{(0-\infty)}$ ,  $AUC_{(0-24)}$ , and  $AUC_{(0-last)}$  will be estimated using the Linear Up Log Down calculation method. Since the calculated concentrations used at each timepoint will be based on measurements from multiple participants, nominal timepoints will be used when estimating these parameters.

The population estimates of AUC(0-24), AUC(0-t), AUC(0- $\infty$ ), Cmax, Tmax, and t1/2 for apramycin in ELF and AM will be presented in Table 89. The population estimates of Cmax, AUC(0- $\infty$ ), AUC(0-24), and AUC(0-last) in plasma, ELF, and AM, as well as the ratios of ELF-to-plasma and AM-to-plasma exposure parameters will be presented in Table 90 for total apramycin.

# 11. IMMUNOGENICITY

There are no immunogenicity endpoints in this trial.

# 12. OTHER ANALYSES

No applicable.

### **13. REPORTING CONVENTIONS**

The mean, median, SD, and other statistics will be reported to 1 decimal place greater than the original data. The min and max will use the same number of decimal places as the original data. Proportions will be presented to 2 decimal places; values greater than zero but < 0.01 will be presented as "<1". Percentages will be reported to the nearest whole number; values greater than zero by < 1% will be presented as "<1"; values greater than 99% but less than 100% will be reported as ">99%".

For PK parameters, AUCs will be reported using 3 significant digits.  $t^{1/2}$ ,  $T_{max}$ , CL, and  $V_d$  values will be reported using 2 significant digits. Ke values will be reported to 3 significant digits. Cmax will be reported with the same number of significant digits as the measurement.

Listings of individual participant data will include a Participant ID column. The participant identifiers assigned by site staff are replaced throughout this report with the Study Data Tabulation Model (SDTM) variable USUBJID to protect the confidentiality of those who volunteered to participate in this protocol. USUBJID has been created as a composite of the 3-letter EDC platform code followed by a numeric identifier assigned chronologically to enrolled participants as well as Screening failures across all sites and protocols in the EDC platforms. Any data sharing activities will include the USUBJID and not the participant identifiers assigned at the study site.

# 14. TECHNICAL DETAILS

SAS version 9.4 or above or R version 4.1 or above will be used to generate all tables, figures, and listings. PK parameters will be estimated through NCA using Phoenix® WinNonlin version 8.2 or later.

# 15. SUMMARY OF CHANGES IN THE CONDUCT OF THE STUDY OR PLANNED ANALYSES

If there are any changes to the planned analysis prior to final data lock and after finalization of the SAP, they may be added to the SAP as an addendum. The SAP will not be amended after final data lock.

# 17. LISTING OF TABLES, FIGURES, AND LISTINGS

Table, figure, and listing shells are presented in Appendix 1, Appendix 2 and Appendix 3.

#### 9.5.1 Pharmacokinetic and Safety Measurements Assessed and Flow Chart

#### Table 2:Schedule of Study Procedures

	Out- patient	In- patient	In- patient		Treatment Period (In-patient)								Follow-up (out-patient)						
Procedures and Evaluations	Day -28 to -3	Day -2	Day -1	Day 1 Day 2 Day 3										ay 3	Day 14	Day	Early Termina-	Unsche-	
	Screening 	Check-in	Baseline	Pre- dose	0 h (dose)	0.5 h (±5 min)	1 h (±5 (min)	2 h (±5 min)	4 h (±10 min)	8 h (±15 min)	16 h (±15 min)	24 h (±1 h)	36 h (±1 h)	48 h (±1 h)	60 h (±1 h)	(± 3 days)	$\begin{array}{c} 3 \\ (\pm 4) \\ (\pm 4) \\ (ays) \end{array}$	tion	duled
Informed consent	Х																		
Demographics	Х																		
Inclusion and exclusion criteria	X 																		
Review of Inclusion and exclusion criteria 		X 	X 	X 															
Medical history (including family history of auditory loss, renal disorders and sudden death)	X																		
Medical History update 		X 4	X 4	X 4															
Prior medication	Х	Х	Х	Х															
Concomitant medication					Х	Х	Х	Х	Х	Х	Х	Х	Х	Х	Х	Х	Х	Х	Х
Complete Physical examination (PE)	Х	Х													X	Х		Х	
Abbreviated PE			Х																
Symptom-directed (Focused) PE				X	Х	Х	Х	Х	Х	Х	Х	Х	X	Х	X		X	Х	X
Vital signs (BP, HR, RR, T) 	Х	Х	Х	Х		Х	Х		Х		Х	Х	Х	Х	Х	Х		Х	Х
Height, Weight, BMI calculation	Х																		
Weight		Х														Х		Х	
Spirometry (FEV1 and FEV1/FVC)	Х																		
12-lead ECG (single recording) 	Х	Х										Х	Х	Х	Х	Х		Х	Х
12-lead ECG (triplicate recording) 			X 7	X 			X 7		X 7		X 7								
Viral Serology 	Х																		
Alcohol breathalyzer test	Х	Х																	
Urine drug toxicity and cotinine	Х	Х																	
Clinical laboratory tests 9	Х	Х		Х								Х		Х		Х		Х	Х
Calculation of glomerular filtration rate (CKD-EPI) 	X	Х		Х								Х		х		Х		X	
Urinalysis 	Х	Х		Х								Х		Х		Х		Х	Х
Serum $\beta$ -HCG pregnancy test (females only)	Х																		
Serum FSH (post-menopausal females only)	Х						1			1		1							

#### Table 2:Schedule of Study Procedures (Continued)

	Out- patient	In- patient	In- patient		Treatment Period (In-patient)									Follow-up (out-patient)		Farly			
Procedures and Evaluations	Day -28 to -3	Day -2	Day -1		Day 1						Day 2 Day 3			ay 3	Day 14	Day	Early Termina-	Unsche- duled	
	Screening 	Check-in	Baseline	Pre- dose	0 h (dose)	0.5 h (±5 min)	1 h (±5 min)	2 h (±5 min)	4 h (±10 min)	8 h (±15 min)	16 h (±15 min)	24 h (±1 h)	36 h (±1 h)	48 h (±1 h)	60 h (±1 h)	(± 3 days)	(±4 days)	tion	uuicu
Urine pregnancy test (females only)		Х																	
Blood sample for exploratory biomarkers 		Х		Х										Х		Х	Х	Х	
Urine sample for exploratory biomarkers 		Х		Х										Х		Х	Х	Х	
Ear otoscopy, Valsalva test, tympanometry, stapedial reflexes	Х																		
Ear otoscopy		Х													Х	Х	Х	Х	
Ear audiometry and otoacoustic tests 	Х	Х													Х	Х	Х	Х	
Admission 		Х																	
Enrollment and Assignment to T cohorts 			Х																
Discharge 															Х				
IV administration of apramycin 					X	21													
Check of infusion site					Х	Х	Х				Х	Х	Х	Х	Х	Х		Х	
Treatment- emergent adverse events (TEAE) and serious AEs (SAEs) 					Х	Х	Х	х	Х	Х	Х	Х	Х	Х	Х	Х	Х	Х	Х
Blood (plasma) sampling for apramycin PK 				Х		Х	Х	Х	Х	Х	Х	Х	Х	Х	Х			Х	
Protein Binding Test 						Х							Х						
Administration of sedative or anesthetic medication 						Х		Х	х	х		Х							
Bronchoscopy /BAL for ELF and AM PK) 						Х		Х	Х	Х		Х							
Oxygenation support (TBC)					Х	Х	Х	Х	Х	Х	Х	Х							
Drinking schedule 					Х	Х	Х	Х	Х	Х	Х	Х	Х	Х				Х	
Counseling 	Х	Х	Х	Х	Х	Х	Х	Х	Х	Х	Х	Х	Х	Х	Х	Х		Х	

. Screening including Ear -Nose-Throat (ENT)/Audiology assessments are planned to be completed in a single Screening Visit. If schedule cannot be accommodated, ENT/Audiology assessments will be completed on a second visit within the screening period.

. Inclusion and exclusion criteria regarding ENT/Audiology assessments to be reviewed by audiologist.

. Review of inclusion and exclusion criteria on Day -2 to determine eligibility for admission; on Day -1, before 12-lead ECG, to determine eligibility for enrollment; and on Day 1 pre-dose to confirm the participant remains eligible for dosing.

 Medical history update to include pre-dose events.

. Vital signs include systolic and diastolic BP, heart rate, respiratory rate and oral temperature.

. 12-lead ECG single recording with 10 sec rhythm strip.

#### Table 2: Schedule of Study Procedures (Continued)

	Out- patient	In- patient	In- patient		Treatment Period (In-patient)									Follov (out-pa	w-up atient)				
Procedures and Evaluations	Day -28 to -3	Day -2	Day -1	Day 1							Day 2 Day 2			ay 3	Day 14	Day	Early Termina-	Unsche-	
	Screening 	Check-in	Baseline	Pre- dose	0 h (dose)	0.5 h (±5 min)r	1 h (±5 nin) r	2 h (±5 nin)	4 h (±10 min)	8 h (±15 min)	16 h (±15 min)	24 h (±1 h)	36 h (±1 h)	48 h (±1 h)	60 h (±1 h)	(± 3 days)	50 (±4 days)	tion	uncu

. 12-lead ECG: triplicate safety ECGs with 10 sec rhythm strips on Day -1 at the same timepoints as the projected timepoints for ECGs to be recorded on Day 1 within 30 min of dosing, and at 1h ( $\pm$  5 min), 4h ( $\pm$  10 min) and 16 h ( $\pm$  15 min) after starting the apramycin dose). Record ECG before VS and PK draws and, at 4 h post-dosing, before administration of sedation or anesthetic for BAL in cohort T3.

. Hepatitis B surface antigen (HBsAg), hepatitis virus C antibody (HCV) and human immunodeficiency virus (HIV) antibody.

. Clinical laboratory tests under fasting conditions: hematology, coagulation, and clinical chemistry panels and thyroid stimulating hormone (TSH) & free T3/free T4.

. The CKD-EPI equation, expressed as a single equation, is  $GFR = 141 \times min(Scr/\kappa, 1)\alpha \times max(Scr/\kappa, 1)-1.209 \times 0.993$ Age  $\times 1.018$  [if female] \_ 1.159 [if black], where Scr is serum creatinine,  $\kappa$  is 0.7 for females and 0.9 for males,  $\alpha$  is -0.329 for females and -0.411 for males, min indicates the minimum of Scr/ $\kappa$ or 1, and max indicates the maximum of Scr/ $\kappa$  or 1 [Levey 2009].(Formula will be used and result will be included in the lab report)

. Urinalysis (UA) by dipstick. If abnormal for blood, protein and glucose, perform microscopic UA. The results of microscopic UA supersede those of UA by dipstick. UA may be postponed in a menstruating female. Abnormal UA in a menstruating female is not graded as a TEAE; the UA should be completed after the end of menstruation.

. Cystatin C in serum.

 Kidney-injury molecule 1 (KIM-1) in urine.

 Pure-tone audiometry with standard frequencies and distortion product otoacoustic emissions (DPOAEs) AE assessments at screening. Pure-tone audiometry including high frequencies and DPOAEs at check-in (Day -2) and at Days 3, 14 (± 3 days), and 30 (± 4 days), or ET.

 Participants will be admitted to the ward on Day -2 after confirmation of eligibility.

 Assignment to Lung PK timepoint cohorts (T1 – T5) and Enrollment to be performed before 12-lead ECG on Day -1 - Participants with ECGs on Day-1 and pre-dose on Day 1 with clinically significant abnormalities according to the PI should not be eligible for receiving study drug and should be withdrawn and replaced.

 Participant may be discharged from the CTU after Day 3 collection of the 60-h plasma PK sample.

.Duration of a pramycin infusion is  $30 \pm 5$  min.

. Adverse events from the start of dosing to the end of the trial are considered treatment-emergent adverse events (TEAE) or serious AEs (SAE).

. Blood samples for plasma PK are taken pre-dose, and at 30 ( $\pm$  5) minutes (end of infusion) and 1 h ( $\pm$ 5 min), 2 h ( $\pm$ 5 min), 4 h ( $\pm$ 10 min), 8 h ( $\pm$ 15 min), 16 h ( $\pm$ 15 min), 24 h ( $\pm$ 1 h), 36 h ( $\pm$ 1 h), 48 h ( $\pm$ 1 h) and 60 h ( $\pm$ 1 h) after start of the infusion - Blood samples for plasma PK are taken at the nominal timepoints. If collection of BAL is delayed, plasma PK will be collected at the nominal timepoint and again 5 min after collection of the last BAL sample. In that case, total apramycin concentration will be measured in both samples, but only the drug concentration in the delayed plasma PK sample will be used to calculate the Lung PK/Plasma PK ratio.

 $^{21}$ . A protein binding test for the measurement of free apramycin will be performed using aliquots of plasma PK samples collected at 0.5 h (± 5 min) and 36 h (± 1 h) after start of infusion.

. Type of sedation or light anesthesia medication for bronchoscopy/BAL procedure and local anesthetic TBD by the anesthesia and bronchoscopy protocols.

. Each participant is assigned to a single bronchoscopy/BAL procedure. Lung PK samples (for measurement of total apramycin concentration) after initiation of infusion and corresponding cohorts (T) are: (Cohort T1), 30 min ( $\pm 5$  min); (Cohort T2), 2 h ( $\pm 5$  min); (Cohort T3), 4 h ( $\pm 10$  min); (Cohort T4), 8h ( $\pm 15$  min); and (Cohort T5), 24 h ( $\pm 1$  h). Lung PK timepoints are aligned with plasma PK samples for measurement of total and free apramycin concentration at 30 min ( $\pm 5$  min), 2 h ( $\pm 5$  min), 4 h ( $\pm 10$  min), 8 h ( $\pm 15$  min) and 24 h ( $\pm 1$  h) after start of apramycin infusion. If BAL is delayed, plasma sample will be collected at the nominal timepoint and again within 5 minutes after the last BAL sample collection. Urea will be measured at the same timepoints in plasma and BAL (ELF) samples.  Participants to be kept hydrated water starting 30 min before until 24 h after start of infusion (document time and volume of water intake).

. Provide counseling at the end of each encounter with the participant. Counsel on use of contraception (males and females), avoidance of pregnancy (women of childbearing potential), avoidance of sperm donation, and avoidance of prohibited medications, illicit drugs, alcohol, nicotine products, vigorous exercise, and exposure to loud noises.

